5.1.3 Other Modality(ies) or Procedures: N/A

5.2 **Definition of Dose-Limiting Toxicity**

The primary endpoint is the maximum tolerated dose (MTD), which is the highest dose level where 1 or fewer of 6 participants experience a dose limiting toxicity (DLT) during the first two combined cycles of treatment. The recommend phase 2 dose (RP2D) is the same as the MTD.

NCI Protocol #:10009

Version Date: 09/04/2020

The maximally administered dose is the dose at which two or more of 6 participants experience a

DLT.

DLT will be defined as the occurrence of any of the following during the first 2 cycles of combined therapy unless the event can clearly be determined to be unrelated to the study drugs.

- Any grade 3 or 4 non-hematologic toxicity with the following exceptions: A) Transient laboratory abnormalities that can be treated or resolve to grade 2 or less within 72 hours.
- Grade 4 hematologic toxicity, including treatment-associated aplasia lasting >42 days from the last dose of study drug. Given that severe anemia, neutropenia and thrombocytopenia are features of advanced MDS and commonly encountered in this patient population, they will not be used to define DLT except if associated with prolonged treatment-associated aplasia as described above.
- Patients with grade 3 immune related adverse events will be removed from the treatment and this will be considered to be a DLT as well as any other immune-related adverse event that results in pembrolizumab interruption, dose modification, or discontinuation of therapy.

Participants who do not complete the first 2 cycles of combined therapy without experiencing a DLT (as DLT period is defined in the first 2 combined therapy cycles) during dose escalation will also be replaced. To be DLT-evaluable, the patient must complete the first two cycles of combined therapy without experiencing a DLT. Any patient who is dose reduced during the entinostat run-in first cycle due to entinostat-related toxicity will be analyzed on the dose level that corresponds to the reduced dose level delivered during the first cycle of combined therapy.

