5.5 Duration of Therapy

In the absence of treatment delays due to adverse event(s), treatment may continue for one year (maximum 18 cycles or entinostat and maximum 17 cycles of pembrolizumab (MK-3475)) or until one of the following criteria applies:

- Disease progression as defined in modified IWG-2006 ([Appendix A1](#), [Appendix A2](#)) for MDS
- If disease has shown evidence of progression based on an increase in the blast counts according to the modified IWG-2006, but the patient is otherwise clinically stable and his transfusion requirement have not changed, the investigator can give two additional cycles of combined treatment and bone marrow biopsy will be repeated after that cycle. If repeat bone marrow biopsy confirms disease progression, the patient will be taken off the trial.
- Intercurrent illness that prevents further administration of treatment
- Patient decides to withdraw from the study
- General or specific changes in the patient's condition render the patient unacceptable for further treatment in the judgment of the investigator

- Clinical progression
- Patient non-compliance
- Pregnancy
 - All women of child bearing potential should be instructed to contact the investigator immediately if they suspect they might be pregnant (e.g., missed or late menstrual period) at any time during study participation.
 - The investigator must immediately notify CTEP in the event of a confirmed pregnancy in a patient participating in the study.
- Termination of the study by sponsor
- The drug manufacturer can no longer provide the study agent
- Unacceptable adverse event(s), including:
 - Any Grade 2 drug-related uveitis or eye pain or blurred vision that does not respond to topical therapy and does not improve to Grade 1 severity within the re-treatment period OR requires systemic treatment.
 - Grade 3 drug-related autoimmune or inflammatory event including uveitis, pneumonitis, diarrhea, colitis, neurologic adverse events, hypersensitivity reaction, or infusion reaction of any duration requires discontinuation.
 - Any Grade 3 or 4 drug-related laboratory imbalance or electrolyte abnormality, not associated with underlying organ pathology and that do not require treatment except for electrolyte replacements, do not require treatment discontinuation, with the following exceptions with approval of the Principal Investigator:

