5.8 Criteria to Resume Treatment

For non-autoimmune or inflammatory events, patients may resume treatment with study drug when the drug-related AE(s) resolve to Grade ≤ 1 or baseline value, with the following exceptions:

- Patients may resume treatment in the presence of Grade 2 fatigue.
- Patients with baseline Grade 1 AST/ALT or total bilirubin who require dose delays for reasons other than a 2-grade shift in AST/ALT or total bilirubin may resume treatment in the presence of Grade 2 AST/ALT OR total bilirubin.
- Patients with combined Grade 2 AST/ALT AND total bilirubin values meeting study parameters outlined in Section 5.4 should have treatment permanently discontinued.
- Non-drug-related toxicity including hepatic, pulmonary toxicity, diarrhea, or colitis, must have resolved to baseline before treatment is resumed.
- Drug-related endocrinopathies (not including drug-related adrenal insufficiency or hypophysitis) adequately controlled with only physiologic hormone replacement may resume treatment after replacement correction and clinically stable regimen.

If the criteria to resume treatment are met, the patient should restart treatment no sooner than the next scheduled time point per protocol. However, if the treatment is delayed past the next scheduled time point per protocol, the treatment should resume at the earliest convenient point that is within the 12 week delay period.

If treatment is delayed >12 weeks, the patient must be permanently discontinued from study therapy, except as specified in [Section 5.4](#) (Duration of Therapy).

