6.2.2 Supportive care guidelines

Based on the severity of the adverse reaction, KEYTRUDA will be withheld and corticosteroids administered. Upon improvement to Grade 1 or less, corticosteroid taper will be initiated and continued to taper over at least 1 month. Based on limited data from clinical studies in patients whose immune-related adverse reactions could not be controlled with corticosteroid use, administration of other systemic immunosuppressants can be considered. KEYTRUDA will be resumed when the immune-mediated adverse reaction remains at Grade 1 or less following corticosteroid taper. KEYTRUDA will be permanently discontinue for any Grade 3 immune-mediated adverse reaction that recurs and for any life-threatening immune-mediated adverse reaction. The following clinically significant, immune-mediated adverse reactions occurred in less than 1% (unless otherwise indicated) of 2799 patients treated with KEYTRUDA: arthritis (1.5%), exfoliative dermatitis, bullous pemphigoid, rash (1.4%), uveitis, myositis, Guillain-Barré syndrome, myasthenia gravis, vasculitis, pancreatitis, hemolytic anemia, and partial seizures arising in a patient with inflammatory foci in brain parenchyma.”

See complete Keytruda prescribing information, especially regarding permanent discontinuation for any Grade 3 immune-mediated adverse reaction that recurs.

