Colitis 
• Colitis• Colitis microscopic• Enterocolitis• Enterocolitis, hemorrhagic• Gastrointestinal (GI) perforation• Intestinal obstruction• Necrotizing colitis• Diarrhea	Grade 2 Diarrhea/Colitis (4-6 stools/day over baseline, dehydration requiring intravenous (IV) fluids <24 hours, abdominal pain, mucus or blood in stool)	Hold pembrolizumab (MK-3475).	
 • Symptomatic treatment • For Grade 2 diarrhea that persists for >3 days, and for diarrhea with blood and/or mucus: 
 - Consider GI consultation and endoscopy to confirm or rule out colitis; and - Administer oral corticosteroids (prednisone 1-2 mg/kg once daily or equivalent). • When symptoms improve to ≤Grade 1, steroid taper should be started and continued over no less than 4 weeks. • Permanently discontinue for inability to reduce corticosteroid dose to ≤10 mg of prednisone or equivalent per day within 12 weeks. • If symptoms worsen or persist >3 days treat as Grade 3
	Grade 3 Diarrhea/Colitis (or Grade 2 diarrhea that persists for >1 week)	Hold pembrolizumab (MK-3475).	
 • Rule out bowel perforation. Imaging with plain films or computed tomography (CT) can be useful. • Recommend consultation with Gastroenterologist and confirmation biopsy with endoscopy. • Treat with IV steroids (methylprednisolone 125 mg) followed by high dose oral steroids (prednisone 1 to 2 mg/kg once per day or dexamethasone 4 mg every 4 hours). When symptoms improve to ≤Grade 1, steroid taper should be started and continued over no less than 4 weeks. Taper over 6 to 8 weeks in patients with diffuse and severe ulceration and/or bleeding. • Permanently discontinue for inability to reduce corticosteroid dose to ≤10 mg of prednisone or equivalent per day within 12 weeks. • If IV steroids followed by high dose oral steroids does not reduce initial symptoms within 48 to 72 hours, consider treatment with additional anti-inflammatory measures as described in the literature^a. Discontinue additional anti-inflammatory measures upon symptom relief and initiate a prolonged steroid taper over 45 to 60 days. If symptoms worsen during steroid reduction, initiate a retapering of steroids starting at a higher dose of 80 or 100 mg followed by a more prolonged taper and administer additional anti-inflammatory measures as needed.

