irAEs	Toxicity grade (CTCAE V5.0)	Action with pembrolizumab	Corticosteroid and/or other therapies	Monitoring and follow-up
Pneumonitis	Grade 2	Withhold	
 • Administer corticosteroids (initial dose of 1 - 2 mg/kg prednisone or equivalent) followed by taper • Add prophylactic antibiotics for opportunistic infections 	
 • Monitor participants for signs and symptoms of pneumonitis • Evaluate participants with suspected pneumonitis with imaging and initiate corticosteroid treatment if indicated
	Recurrent Grade 2, Grade 3 or 4	Permanently discontinue		
Diarrhea / Colitis	Grade 2 or 3	Withhold	
 • Administer corticosteroids (initial dose of 1 - 2 mg/kg prednisone or equivalent) followed by taper 	
 • Monitor participants for signs and symptoms of diarrhea (eg, bloody diarrhea, abdominal pain, fever) and of bowel perforation (ie, peritonitis) • Participants with \geqGrade 2 diarrhea should consider GI consultation and performing colonoscopy • Participants with diarrhea/colitis should be encouraged to drink small quantities of clear fluids. If sufficient oral fluids are not tolerated, parenteral fluids and electrolytes should be considered
	Recurrent Grade 3 or Grade 4	Permanently discontinue		
AST or ALT elevation or Increased Bilirubin	Grade 2 ^a	Withhold	
 • Administer corticosteroids (initial dose of 0.5 - 1 mg/kg prednisone or equivalent) followed by taper 	

Version Date: 09/04/2020			prednisone or equivalent) followed by taper	
 Monitor with liver function tests (concurrently until liver enzyme value re
	Grade 3 ^b or 4 ^c	Permanently discontinue	
 Administer corticosteroids (initial dose of 1 - 2 mg/kg prednisone or equivalent) followed by taper 	
Type 1 diabetes mellitus (T1DM) or Hyperglycemia	New onset T1DM or Grade 3 or 4 hyperglycemia associated with evidence of β -cell failure	Withhold ^d	
 Initiate insulin replacement therapy for participants with T1DM Administer anti-hyperglycemic in participants with hyperglycemia 	
 Monitor participants for hyperglycemic symptoms of diabetes

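### Pembrolizumab stopping rules conflict for a first Grade 3 immune colitis, Grade 3 myocarditis and some Grade 4 immune events, and no text expressly says which rule prevails

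*Combined protocol and SAP*

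**What the plan says.** Section 5.5 lists the unacceptable adverse events that end treatment. For Grade 3 immune or inflammatory events its rule ends "diarrhea, colitis, neurologic adverse events, hypersensitivity reaction, or infusion reaction of any duration requires discontinuation". Section 5.2, in the DLT definition, agrees: "Patients with grade 3 immune related adverse events will be removed from the treatment". Section 5.8 opens its general route back to treatment for a different class of event: "For non-autoimmune or inflammatory events, patients may resume treatment with study drug when the drug-related AE(s) resolve". It adds one endocrine exception: "Drug-related endocrinopathies (not including drug-related adrenal insufficiency or hypophysitis) adequately controlled with only physiologic hormone replacement may resume treatment".

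Section 6.2.2 says otherwise: "KEYTRUDA will be resumed when the immune-mediated adverse reaction remains at Grade 1 or less following corticosteroid taper". Permanent stopping is narrower there: "KEYTRUDA will be permanently discontinue for any Grade 3 immune-mediated adverse reaction that recurs and for any life-threatening immune-mediated adverse reaction".

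Section 6.2.3 holds several tables. The AE-specific table (graded by CTCAE v4.0) has a row for "Grade 3 Diarrhea/Colitis (or Grade 2 diarrhea that persists for >1 week", and its action is to hold. The later immune-event table (CTCAE v5.0) withholds for Grade 2 or 3 diarrhea/colitis and stops permanently only for "Recurrent Grade 3 or Grade 4".

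Section 5.5 also lists, as a separate bullet, any patient who needs systemic steroids or other immunosuppression. Its stated exceptions cover hypophysitis, skin-only toxicity and peripheral thyroiditis.

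**The concern.** For a first Grade 3 immune colitis, the section 5.5 rule and the section 6.2.2 rule are both worded as instructions, and one patient cannot satisfy both. A site working from 5.5 stops pembrolizumab for good; a site working from 6.2.2 gives it again. The same kind of split appears for Grade 3 myocarditis and for some Grade 4 immune events.

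At stake are re-exposure to a checkpoint inhibitor after a severe immune reaction, and consistency between sites. The synopsis notes that the combination had not been studied clinically in MDS, so there is little outside experience for an investigator to fall back on.

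**Working it through.** The plan gives no figure on this point, so the check sets the rules side by side.

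| Event | Text that stops pembrolizumab | Text that holds or allows return |
|---|---|---|
| First Grade 3 immune diarrhea/colitis | 5.5 (any duration); 5.2 (DLT definition) | 6.2.2 (resumed after taper); 6.2.3 AE-specific table (hold); 6.2.3 v5.0 table (withhold) |
| Grade 3 myocarditis | 6.2.3 v5.0 table (permanent); 5.5, whose list is not exhaustive | 6.2.3 AE-specific table (hold, restart permitted) |
| Grade 4 immune event not in the AE-specific table | 6.2.3 v5.0 table, row for all other immune events (permanent); 6.2.2 if life-threatening | 6.2.3 general table (withhold; stop only if steroids cannot be reduced in time) |

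In the first row the outright clash is 5.5 against 6.2.2. The two colitis rows in 6.2.3 leave open a rechallenge that 5.5 rules out. Section 5.2 does not settle it: its rule sits in a definition that covers the first 2 combined cycles, and pembrolizumab may run to 17, leaving 17 − 2 = 15 cycles outside that window. Grade 3 uveitis is a related mismatch: 5.5 names it as requiring discontinuation, while the AE-specific table holds and asks only that permanent stopping be considered.

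**Systemic-steroid bullet in 5.5.** The general table in 6.2.3 indicates systemic steroids for Grade 3 and 4 immune events, and the AE-specific table gives them for Grade 3 myocarditis. Read literally, the bullet therefore stops all of these. It also stops Grade 2 pneumonitis, hepatitis, nephritis and persistent diarrhea, which 6.2.3 manages with a hold and steroids. It adds to the conflict.

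**Steroid-reduction deadline** (time to get down to about 10 mg/day of prednisone), counted by statement:

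- 12 weeks: hypophysitis in 5.5 (1), general table in 6.2.3 (1), AE-specific table (14). Total 1 + 1 + 14 = 16. The 14 are colitis 2, thyroid 1, hypophysitis 1, hematologic 2, hepatic 2, neurologic 1, ocular 1, pneumonitis 1, renal 1, skin 1, other events 1.
- 1 month: item 2 of the general instructions ahead of the v5.0 table (1).
- No time given: skin-only bullet in 5.5 (1).
- Sum: 16 + 1 + 1 = 18.

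The clock also starts differently: from the toxicity in the general table, from stopping pembrolizumab in item 2.

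**Is there a precedence rule?** Section 5.7 makes 5.5 the reference for removal from study but does not mention 6.2. Section 6.2.3 describes its AE-specific recommendations as guidelines subject to judgment; that statement does not reach 6.2.2. Section 6 asks for the conservative course when causality is uncertain, which is a different question. None of these expressly decides between the rules above.

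**Effect on the primary endpoint.** Section 5.2 counts a Grade 3 immune event as a DLT, and also any other immune event that leads to pembrolizumab being interrupted or discontinued. Holding and stopping therefore give the same DLT count.

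**The case against.** The best defense is that the order is clear enough in practice. Section 5.5 is mandatory in wording, 5.7 sends the reader to it, and 6.2 presents itself as guidelines. The v5.0 table looks like the newer text: section 7.2 moves AE reporting to v5.0 from April 2018, and this protocol version is dated 09/04/2020. On that view the myocarditis clash is leftover v4.0 text, and 5.5 already agrees with the v5.0 row. Dosing questions can also be raised on the calls with the CTEP Medical Officer, held at least monthly (section 12.1).

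Much of this stands as a guide to intent, but it does not remove the conflict. Nothing retires the v4.0 table. If the v5.0 table did supersede it, that table would still only withhold for a first Grade 3 colitis, against 5.5. Section 6.2.2 is itself worded as an instruction.

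Three stronger readings are tempting and not supported. A reader might infer that 5.5 is silent on Grade 4 events because its rule names Grade 3; the systemic-steroid bullet reaches them if taken literally. A reader might infer that 12 weeks is the intended deadline because 16 of 18 statements say so; 14 of those are one sentence repeated in the v4.0 table, and the 1-month limit may be the update. A reader might infer that the skin-only bullet leaves no limit at all; 5.5 and 5.8 cap drug-related dosing interruptions at 12 weeks, and the Grade 3 skin row states 12 weeks.

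**Conclusion.** The conflict is real. Three severe event types have opposite stated outcomes, and the steroid deadline differs between 12 weeks and 1 month. This should be corrected by amendment because a patient could be given pembrolizumab again after an event that another rule in the same protocol says must end treatment.

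A reader might infer that the DLT count, the MTD or the response rate is compromised. The documents do not support that: interruption and discontinuation for an immune event both count within the DLT window, and nothing in the plan allows a shift in response rate to be derived. Nor can the number of patients affected be derived. The conclusion rests on the wording as it stands and assumes no separate instruction to sites on precedence.

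**What to change.** Make targeted edits rather than adding a general clause that the stricter rule wins. Such a clause would bring the systemic-steroid bullet into play and could make permanent stops of Grade 2 events that 6.2.3 means to hold and taper.

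1. In 6.2.3, change Grade 3 myocarditis in the AE-specific table, and Grade 4 in the general immune-event table, to permanent discontinuation, matching the v5.0 table.
2. Bring 6.2.2, both Grade 3 diarrhea/colitis rows and the Grade 3 uveitis row into line with 5.5. If the sponsor prefers to allow rechallenge after a first Grade 3 colitis, that is a safety decision to be stated in 5.5 and 5.2.
3. Keep the exceptions for hypophysitis, skin-only toxicity, thyroiditis and endocrinopathies controlled on hormone replacement.
4. State that the systemic-steroid bullet in 5.5 does not by itself permanently stop a Grade 2 event that 6.2.3 manages with a hold and taper.
5. Have the sponsor confirm one steroid deadline and one start point, without presuming 12 weeks.
6. Say whether a patient stopped for a 5.5 event may continue entinostat alone. The synopsis allows the non-causative drug to continue when causality is clear; 5.7 removes from study a patient who meets a 5.5 criterion.

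The cost is a protocol amendment, with no change to sample size, visits or analyses. It does settle clinical policy, so it needs the sponsor's medical decision. Some patients who might have been rechallenged will stop pembrolizumab; the documents do not let that number be derived.

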3.1.2 Age ≥ 18 years

Because no dosing or adverse event data are currently available on the use of entinostat in combination with pembrolizumab (MK-3475) in patients <18 years of age, children are excluded from this study, but will be eligible for future pediatric trials.

3.1.3 ECOG performance status ≤ 2 ([Appendix C](#)).

3.1.4 Patients must have laboratory test results within these ranges:

- Calculated creatinine clearance by MDRD (CrCl) $= >60$ ml/min/1.73 squared meter
- Total bilirubin ≤ 2.0 mg/dL unless due to Gilbert's syndrome, hemolysis, or ineffective hematopoiesis and AST (SGOT) and ALT (SGPT) $\leq 3 \times$ ULN

3.1.5 Females of childbearing potential must have a negative serum or urine pregnancy test within 72 hours prior to start of first cycle of therapy.

- Patients must have no clinical evidence of CNS or pulmonary leukostasis, disseminated intravascular coagulation, or CNS leukemia.
- Patients must have no serious or uncontrolled medical conditions

3.1.6 The effects of entinostat and pembrolizumab (MK-3475) on the developing human fetus are unknown. For this reason, women of child-bearing potential and men who are sexually active with women of childbearing potential must agree to use adequate contraception (hormonal or barrier method of birth control; abstinence) prior to study entry and for the duration of study participation. Should a woman become pregnant or suspect she is pregnant while she or her partner is participating in this study, she should inform her treating physician immediately. Men who are sexually active with women of childbearing potential, treated or enrolled on this protocol must also agree to use adequate contraception prior to the study, for the duration of study participation, and 4 months after completion of entinostat and MK3475 (pembrolizumab) administration.

3.1.7 Ability to understand and the willingness to sign a written informed consent document.

3.1.8 Patients, who relapsed 6 months after bone marrow transplant and have no evidence of active graft versus host disease and are off systemic immunosuppressant medications for at least 2 months and have received HMA therapy before or after transplant and meet other eligibility criteria of progression after at least 4 months of DNMTi therapy, are eligible to be enrolled in this clinical trial.

3.1.9 Patients who are Human Immunodeficiency Virus (HIV) positive may participate IF they meet the following eligibility requirements:

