 - Grade 2-4 hypophysitis or pan-hypopituitarism requires holding pembrolizumab (MK-3475) and discontinuing treatment if unable to reduce corticosteroid dose to ≤ 10 mg of prednisone or equivalent per day within 12 weeks.
 - Grade 4 amylase or lipase abnormalities that are not associated with diabetes mellitus, associated liver or gall bladder inflammation clinical manifestations of pancreatitis and which decrease to <Grade 4 within 1 week of onset may stay on study.
 - Any drug-related liver function test (LFT) abnormality that meets the following criteria requires discontinuation: Grade 3 AST or ALT ($>5 \times$ ULN) and total bilirubin $>3 \times$ ULN.
 - Grade 3 drug-related thrombocytopenia >7 days or associated with bleeding

requires discontinuation.

- Any patient requiring systemic steroid or other immunosuppressive treatment.
- For patients with skin-only toxicity, when symptoms improve to \leq Grade 1, steroid taper should be started and continued over no less than 4 weeks. Discontinue MK-3475 if unable to reduce corticosteroid dose for irAEs to \leq 10 mg. pembrolizumab (MK-3475) treatment may be restarted and the dose modified as specified in the protocol.
- Patients with peripheral thyroiditis and no other autoimmune/inflammatory event may be restarted after a short course of steroids on a stable replacement regimen.
- Any dosing interruption lasting $>$ 12 weeks with the following exceptions:
 - Dosing interruptions $>$ 12 weeks that occur for non-drug-related reasons may be allowed if approved by the Principal Investigator. Prior to re-initiating treatment in a subject with a dosing interruption lasting $>$ 12 weeks, the Principal Investigator must be consulted.
 - Tumor assessments should continue as per protocol even if dosing is interrupted.

The reason(s) for protocol therapy discontinuation, the reason(s) for study removal, and the corresponding dates must be documented in the Case Report Form (CRF).

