6.2.3 Table of Dose Modifications and Supportive Care Guidelines

The table below includes guidelines for managing irAEs that are not listed in the AE-specific table

General Dose Modification Guidelines for Drug-Related Immune-Related Adverse Events

irAE	Withhold/Discontinue MK-3475?	Supportive Care
Grade 1	No action	Provide symptomatic treatment
Grade 2	May withhold pembrolizumab (MK-3475)	Consider systemic corticosteroids in addition to appropriate symptomatic treatment
Grade 3 and Grade 4	Withhold pembrolizumab (MK-3475) Discontinue if unable to reduce corticosteroid dose to < 10 mg per day prednisone equivalent within 12 weeks of toxicity	Systemic corticosteroids are indicated in addition to appropriate symptomatic treatment. May utilize 1 to 2 mg/kg prednisone or equivalent per day. Steroid taper should be considered once symptoms improve to Grade 1 or less and tapered over at least 4 weeks.

Additionally, pembrolizumab (MK-3475) will be withheld for other drug-related Grade 4 hematologic toxicities, non-hematological toxicity \geq Grade 3 including laboratory abnormalities, and severe or life-threatening AEs.

The table below includes dose modification guidelines for other toxicities that do not appear to be irAEs and are not listed in the AE-specific table.

Dose Modification Guidelines for Other Drug-Related Adverse Events

Toxicity	Grade	Hold Treatment (Y/N)	Timing for restarting treatment	Dose/Schedule for restarting treatment	Discontinue Subject
Hematological Toxicity	1, 2, 3	No	N/A	N/A	N/A
	4	Yes	Toxicity resolves to Grade 0-1 or baseline	May increase the dosing interval by 1 week	Toxicity does not resolve within 12 weeks of last infusion Permanent discontinuation should be considered for any severe or life-threatening event
Non-hematological toxicity Note: Exception to be treated similar to grade 1 toxicity 
Grade 2 alopeciaGrade 2 fatigue For additional information regarding Adverse Events with a potential Immune-Etiology reference Section 6.1.2.	1	No	N/A	N/A	N/A
	2	Consider withholding for persistent symptoms	Toxicity resolves to Grade 0-1 or baseline	Clinical AE resolves within 4 weeks: Same dose and schedule Clinical AE does not resolve within 4 weeks: May increase the dosing interval by 1 week for each occurrence	Toxicity does not resolve within 12 weeks of last infusion

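### Sections 5.5, 5.8 and 6.2.3 disagree on when a liver event ends pembrolizumab for good, and the combined grade 2 stop in 5.8 has no usable trigger

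*Combined protocol and SAP*

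**What the plan says.** **Section 5.5, liver criterion.** "Any drug-related liver function test (LFT) abnormality that meets the following criteria requires discontinuation: Grade 3 AST or ALT" above 5 x ULN, joined by *and* to total bilirubin above 3 x ULN. Nearby, grade 3 or 4 drug-related laboratory abnormalities "not associated with underlying organ pathology and that do not require treatment except for electrolyte replacements, do not require treatment discontinuation", apart from listed exceptions that need Principal Investigator approval.

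**Section 5.5, steroid criterion.** "Any patient requiring systemic steroid or other immunosuppressive treatment" is listed as an unacceptable event. The restart wording that follows concerns skin-only toxicity and thyroiditis, not the liver.

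**Section 6.2.3, AE-specific table, hepatic row (headed CTCAE v4.0).** The row covers autoimmune hepatitis, hepatitis and transaminase elevations. Grade 2 (AST/ALT >3 to 5 x ULN and/or bilirubin >1.5 to 3 x ULN): hold, give steroids, taper, then resume per protocol. Grade 3 (AST/ALT >5 x ULN and/or bilirubin >3 x ULN): discontinue pembrolizumab and give high-dose IV steroids.

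**Section 6.2.3, immune-related AE table (headed CTCAE V5.0).** Raised AST/ALT or bilirubin: withhold at grade 2, permanently discontinue at grade 3 or 4. Its footnotes grade against ULN if baseline is normal and against baseline if it is abnormal. Its general instructions, like Section 6.2.2, allow restart once the event is grade 1 or less after a steroid taper.

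**Section 5.8.** The lead-in reads "For non-autoimmune or inflammatory events, patients may resume treatment with study drug when the drug-related AE(s) resolve to Grade" 1 or less, or to baseline. One exception is: "Patients with combined Grade 2 AST/ALT AND total bilirubin values meeting study parameters outlined in Section 5.4 should have treatment permanently discontinued". Later, after a delay of more than 12 weeks, "the patient must be permanently discontinued from study therapy, except as specified in" Section 5.4, which that sentence labels Duration of Therapy. Section 5.4 is in fact concomitant medication and supportive care; Duration of Therapy is 5.5.

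**The concern.** A site managing a liver event has to know three things: whether to hold, whether to stop, and whether pembrolizumab may be given again. The protocol answers the last of these differently in different places.

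- For a non-immune grade 3 rise in one analyte, 5.5 does not require a stop and 6.2.3 does.
- For a grade 2 hepatic event treated with steroids as 6.2.3 directs, 6.2.2 and 6.2.3 expect restart, but the steroid criterion in 5.5 ends treatment.
- For combined grade 2 values, 5.8 intends a permanent stop, but the condition attached to it leads nowhere.
- For immune-related events in patients who enter with raised values, the two hepatic tables give different thresholds, and the protocol does not say which applies.

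At stake is consistent safety management between sites, and whether a patient loses or keeps further pembrolizumab after recovery.

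**Working it through.** No stated statistical figure is involved. The check sets the rules side by side and applies them to example patients. All values are multiples of ULN unless marked otherwise.

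**Inputs.** 5.5 liver criterion: AST/ALT >5 and bilirubin >3. AE-specific hepatic row: hold at AST/ALT >3 to 5 and/or bilirubin >1.5 to 3; discontinue at >5 and/or >3. Immune-related table: the same multiples, but of baseline when baseline is abnormal. Study Calendar (Section 10) footnote 2 dosing gate, without liver metastases: AST/ALT at most 3, bilirubin at most 2. Entry limits (3.1.4): AST/ALT at most 3 x ULN; bilirubin at most 2.0 mg/dL, with listed exceptions.

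**1. One analyte or both (non-immune, normal baseline, AST 8, bilirubin normal).**
- 5.5: 8 > 5, but bilirubin is not > 3, so the liver criterion is not met. With no organ pathology and no treatment needed, the laboratory exemption can be read to apply.
- AE-specific row: 8 > 5, so discontinue.
- Dosing meanwhile: Section 6.2.3 withholds ("Additionally, pembrolizumab (MK-3475) will be withheld for other drug-related Grade 4 hematologic toxicities, non-hematological toxicity" of grade 3 or higher), and the Calendar blocks both drugs because 8 > 3.
- If the site gives the IV steroids in the grade 3 row, the 5.5 steroid criterion applies and the two sections converge. The gap therefore remains only where the site uses the clinical-judgment clause of the AE-specific table and gives none.
- The grade 3 row says discontinue. It uses the word permanently only for a failed steroid taper, so restart after recovery is not settled there.

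**2. Steroid-treated grade 2 (AST 4, bilirubin normal).** AE-specific row: 3 < 4 ≤ 5, so hold, give steroids, taper and resume. The 5.5 steroid criterion ends treatment. Both cannot be followed.

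**3. Combined grade 2 (non-immune, AST 4, bilirubin 2).**
- AE-specific row: 3 < 4 ≤ 5 and 1.5 < 2 ≤ 3, so hold, then resume per protocol.
- 5.8 read literally: Section 5.4 has no AST, ALT or bilirubin values to meet.
- 5.8 read through 5.5: AST must exceed 5 and bilirubin must exceed 3. The grade 2 ranges (>3 to 5 and >1.5 to 3) do not overlap these at all, so correcting the section number alone does not help.

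**4. Reference level (immune-related, abnormal baseline b).** Immune-related table: hold above 3b, stop above 5b.

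| Baseline AST | AE-specific: hold / stop | Immune-related: hold / stop |
|---|---|---|
| 1.5 | >3 / >5 | >4.5 / >7.5 |
| 2 | >3 / >5 | >6 / >10 |
| 3 (entry limit) | >3 / >5 | >9 / >15 |

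A rise from 3 to 6 is a stop in the first table (6 > 5) and calls for no action in the second (6 < 9). The Calendar gate still prevents dosing (6 > 3). For baseline bilirubin 2 x ULN, the stop is above 3 in the first table and above 3 x 2 = 6 in the second.

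**5. Reach of a repaired 5.8 rule.** Entry bilirubin 2.0 mg/dL, with ULN assumed to be 1.0 to 1.3 mg/dL: 2.0/1.3 = 1.54 and 2.0/1.0 = 2.0. Bilirubin is then already in the grade 2 range, and AST/ALT above 3 x ULN would complete the trigger.

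**The case against.** The strongest answer is that the rules form tiers. Section 5.5 ends all study treatment, while 6.2.3 stops pembrolizumab only; the synopsis lets a patient stay on the non-causative agent when causality is clear. That reading is workable and the fix adopts it, but the liver criterion in 5.5 does not say it.

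A second answer is that the immune-related table is the more specific one and carries the newer CTCAE version, which Section 7.2 applies to AE reporting from April 2018. That is a fair argument for its governing immune-related events. Yet the AE-specific hepatic row also names autoimmune hepatitis, and no sentence sets precedence.

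A third is that a site can take grade 2 limits from 6.2.3 and apply 5.8 sensibly. It can, but only by setting aside the condition as written.

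A reader might infer three stronger things that the documents do not support:
- *Grade 3 immune-related hepatitis could continue on pembrolizumab.* It could not. Section 5.5 separately stops grade 3 drug-related autoimmune or inflammatory events, 5.2 removes such patients from treatment, and the immune-related table makes the stop permanent.
- *Patients would be dosed through abnormal liver tests.* Section 6.2.3 and the Calendar prevent this.
- *The DLT count is materially compromised.* Section 5.2 counts grade 3 or 4 non-hematologic toxicity, apart from transient laboratory changes, whichever stopping rule a site follows.

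**Conclusion.** The inconsistency is real and worth correcting, with modest patient-safety weight. What is unsettled is mainly restart: after a non-immune grade 3 rise in one analyte, and after a steroid-treated grade 2 hepatic event. The combined grade 2 stop in 5.8 has no usable trigger. For immune-related events with an abnormal baseline, the two tables' AST hold and stop levels differ by a factor equal to the baseline multiple, up to 3 at the entry limit.

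This rests on reading the Section 5.4 references in 5.8 as meant for 5.5, which the label in 5.8 itself supports. It does not establish that ULN is the right reference or that baseline multiples are wrong; the documents leave that open. Sample size, power and alpha are unaffected.

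**What to change.** A wording amendment in four parts.

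(a) **Section 5.5.** For stopping pembrolizumab, change *and* to *or*: AST/ALT >5 x ULN or bilirubin >3 x ULN. Keep the both-raised criterion for ending all study treatment, in line with the synopsis provision on the non-causative agent. Exempt from the steroid criterion grade 2 hepatic events that recover and taper as 6.2.2 and 6.2.3 describe, subject to (b).

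(b) **Section 5.8.** Replace the Section 5.4 qualifier with the grade 2 limits: AST/ALT >3 to 5 x ULN and bilirubin >1.5 to 3 x ULN, drug-related and non-immune. Correct the other reference from 5.4 to 5.5.

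(c) **Section 6.2.3, hepatic grade 2.** Point the resume-per-protocol instruction to 6.2.2 and the immune-related table's general instructions for immune-related events, and to 5.8 for the rest. Section 5.8 alone would not do, because its lead-in covers only non-autoimmune events.

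(d) **Precedence.** State which hepatic table governs immune-related events. Whether it uses ULN or baseline multiples is the sponsor's clinical decision.

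After (a) to (c), for non-immune events, AST 8 alone stops pembrolizumab in both sections. AST 4 with bilirubin 2 is held and not resumed. AST 4 alone is held and may resume after recovery.

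The cost is slightly more mandatory pembrolizumab stops. A patient entering with bilirubin near 2.0 mg/dL could also meet the combined grade 2 stop once AST/ALT exceeds 3 x ULN, if the rise is judged drug-related.
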